7.4.2. Secondary Analyses

A number of secondary analyses will be conducted to evaluate the secondary efficacy outcomes. Secondary efficacy parameters include cytokine concentration/markers of inflammation, circulating markers of fibrosis, aldosterone concentration, heart rate variability (sub-study), arrhythmias (sub-study), additional echocardiographic parameters including change in resting and hyperemic myocardial blood flows between baseline and 36 weeks and change in LVMI between 0 and 36 weeks, and coronary flow reserve (CFR) on myocardial PET (sub-study). Analysis for these secondary outcomes will be similar to that for the primary outcome. Distribution of the secondary parameters will be examined and appropriate transformation will be applied.

7.4.3. Interim Analysis

No interim efficacy analysis is planned.

8. Safety and Adverse Events

8.1. Definitions

Definitions are per the January 2007 Guidance on Reviewing and Reporting Unanticipated Problems Involving Risks to Participants or Others and Adverse Events, Office on Human Research Protection (OHRP) Guidance. <http://www.hhs.gov/ohrp/policy/advevntguid.html>

8.1.1. Adverse Event

An *adverse event (AE)* is any untoward or unfavorable medical occurrence in a human study participant, including any abnormal sign (for example, abnormal physical exam or laboratory finding), symptom, or disease, temporally associated with the participant's involvement in the research, whether or not considered related to the participant's participation in the research.

8.1.2. Serious Adverse Event

A *serious adverse event (SAE)* is any AE that is:

- fatal or results in death
- life-threatening
- requires or prolongs hospital stay
- results in persistent or significant disability or incapacity
- results in congenital anomalies or birth defects
- an important medical event*

*Important medical events are those that may not be immediately life threatening, but are clearly of major clinical significance.

8.1.3. Unanticipated Problems Involving Risk to Participants or Others

(See also Section 8.3.4)

An Unanticipated Problem is any incident, experience, or outcome that meets all of the following criteria:

- unexpected (in terms of nature, severity, or frequency) given the research procedures that are described in the IRB-approved research protocol and informed consent document and the characteristics of the participant population being studied;
- related or possibly related to participation in the research; possibly related means that there is a reasonable possibility that the incident, experience or outcome may have been caused by the procedures involved in the research, and
- suggests that the research places participants or others at a greater risk of harm (including physical, psychological, economic, or social harm) related to the research than was previously known or recognized.

8.1.4. Pre-Existing Condition

A preexisting condition is one that is present at the start of the study. A preexisting condition will be recorded as an adverse event if the frequency, intensity, or the character of the condition worsens during the study period.

8.1.5. General Physical Examination Findings

At screening, any clinically significant abnormality will be recorded as a preexisting condition. At the end of the study, any new clinically significant findings/abnormalities that meet the definition of an adverse event will also be recorded and documented as an adverse event.

8.2. Adverse Event Tracking Period

The study period during which adverse events must be tracked and reported is normally defined as the period from the initiation of study procedures to the end of the study treatment follow-up. For this study, the study treatment follow-up is 4 weeks following the last dose of study drug.

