3.1. General Design

This is a randomized, placebo-controlled 4-arm trial that will compare placebo with 3 doses of SPL. Participants will be randomized in a 2:1:1:1 fashion to placebo or SPL, with equal proportions randomized to each of 3 SPL doses: 12.5, 25 or 50 mg once daily. As shown in **Figure 1**, the study will be conducted in 2 phases – a dose escalation phase and a treatment phase.

All participants randomized to SPL will initiate treatment at 12.5 mg daily. Participants will be evaluated weekly for tolerability, hypotension and hyperkalemia. At 2 weeks, if the initial dose has been tolerated, participants randomized to the 25 or 50 mg SPL arm will increase the dose to 25 mg for 2 weeks with weekly evaluation for tolerability, hypotension and hyperkalemia. Participants randomized to 12.5 mg SPL or placebo arm will continue on the same dose with weekly evaluation for tolerability, hypotension and hyperkalemia.

[figure not shown]
At 4 weeks, participants randomized to the 50 mg SPL arm will increase the dose to 50 mg if the 25 mg dose was tolerated with weekly evaluations for tolerability, hypotension and hyperkalemia.

until 6 weeks. Participants randomized to 12.5 mg, 25 mg, or placebo will continue on the same dose with weekly evaluation for tolerability, hypotension and hyperkalemia until 6 weeks.

In order to maintain the blind, during the dose escalation phase all study participants, regardless of randomized assignment, will receive new study drug kits every 2 weeks and will be evaluated weekly.

At the end of the dose escalation phase, participants will continue treatment based on the randomized dose assignment for an additional 30 weeks (treatment phase) such that the total duration of study medication is 36 weeks. As described in **Sections 6.8 and 6.9**, the dose of SPL or placebo will be decreased during the dose-escalation and follow-up phases for hypotension, hyperkalemia or other dose limiting side-effects.

Figure 1. Study Design

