4.4.2. Early Termination of Study Medication

Study medication will be discontinued by the research team in the following circumstances because of the potential for compromising patient safety:

- Allergy to or documented intolerance of study medications
- Poor adherence with dialysis schedule compromising ability to follow serum potassium on a monthly basis
- Organ transplantation
- Change to a different dialysis modality
- Initiation of digoxin therapy
- Transfer to a non-participating dialysis unit

If study medication is discontinued study visits and procedures will continue unless the participant withdraws consent for follow-up.

5. Study Drug

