6.6.1. Early Withdrawal Visit

If a patient withdraws from the trial before the Week 36 milestone or if it becomes known that a participant will not be available for an in-person visit at Week 36 (e.g., due to relocation), an Early Withdrawal visit will be scheduled to conduct the final comprehensive assessments that otherwise would be performed at Week 36. For participants in the heart rhythm monitoring sub-study, the assessments will include heart rhythm monitoring using the Medtronic SEEQ device for 7 continuous days at the time of early withdrawal, if possible. Patients who stop taking study medication are not considered early withdrawals and will be asked to continue to provide follow-up data on the study schedule and to participate in the final comprehensive assessment at Week 36.

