6.7. Week 40 Visit (-7 to +7 days)

At the Week 40 visit (4 weeks after end of treatment), patients will be interviewed in person or by telephone to review the occurrence of adverse events as described in **Section 6.4**. Dialysis unit records will be reviewed for inter-current laboratory values, the occurrence of hypotension, and changes to the dialysis prescription.

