6.9. Hyperkalemia Management

[figure not shown]
Serum potassium will be measured at 3-5 days and 2 weeks after study drug initiation or dose increase as well as monthly throughout the duration of treatment. In order to minimize the risks of hyperkalemia, all participants will be provided with standardized, routine printed dietary information about dietary sources of potassium at the Baseline/Randomization visit. Treating clinicians will continue to manage the dialysate potassium concentration according to local standards. A hyperkalemia management guideline will be provided to treating clinicians. Study staff will monitor potassium values and contact treating clinicians in the event of hyperkalemia to review the management guidelines and ensure that hyperkalemia is being actively managed. Treating clinicians will be free to manage hyperkalemia according to local standards. However, study drug dose reductions or discontinuation will be directly managed by study investigators in accordance with the Hyperkalemia Management algorithm (see **Figure 2**).

As shown in **Figure 2**, study drug will be discontinued if serum potassium is ≥ 7.0 mEq/L. Study drug will also be discontinued if a 3rd study drug dose reduction is required. Study drug dose will be reduced if serum potassium is 6.0 – 6.9 mEq/L and either a) remains ≥ 6.5 mEq/L on repeat measurement or b) remains ≥ 6 mEq/L on repeat measurement despite a dialysate potassium bath concentration of ≤ 2.0 mEq/L. Reversible causes of hyperkalemia should be considered and addressed when serum potassium is ≥ 6.0 mEq/L even if there are changes to study drug dosing. Reversible causes of hyperkalemia include vascular access dysfunction, missed dialysis sessions, shortened or technically compromised dialysis sessions, dietary indiscretion and ACEI or ARB use. In general, these reversible causes should be addressed prior to reducing the dialysate potassium concentration. Use of 1.0 mEq/L dialysate potassium is not recommended. However, treating clinicians are not prohibited from using low potassium dialysate solutions in accordance with local practices. Serum potassium will be rechecked within one week when potassium is ≥ 6.0 mEq/L. Results of serum potassium and recommendations for change in dialysis orders will be conveyed to treating clinicians and the dialysis unit nursing staff.

CONFIDENTIAL

Do not disclose or use except as authorized by the Hemodialysis Novel Therapies Consortium.

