8.3.1. Adverse Events of Interest

The following adverse events are anticipated in patients treated with spironolactone and will be recorded on the appropriate Adverse Event of Interest CRF.

- Hyperkalemia
- Hypotension
- Gynecomastia
- Breast tenderness
- Gastrointestinal symptoms including: diarrhea, constipation, and nausea
- Rash

If the event meets the definition of serious as defined in **Section 8.1.2**, it will be recorded on an SAE form in addition to the appropriate adverse event of special interest CRF.

Participants will be contacted weekly during dose escalation and monthly while on treatment to assess for the occurrence of Adverse Events of Interest. The clinical course of each event will be followed until resolution, stabilization, or until it has been determined that the study treatment or participation is not the cause.

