8.4. Reporting of Serious Adverse Events and Unanticipated Problems

Study sites are required to report SAEs and Unanticipated Problems to the DCC within 24 hours of first knowledge of the event. To report such events, an SAE form or an Unanticipated Problem form will be completed by the investigator and faxed to the DCC. The DCC will facilitate the timely medical review and reporting of the event to the NIDDK, the DSMB, and the study sites in accordance with DSMB-approved study policies and IRB requirements.

The investigator will keep a copy of the SAE form / Unanticipated Problem form on file at the study site. At the time of the initial report, the following information should be provided:

- Study identifier
- Study Center
- Participant number
- A description of the event
- Date of onset
- Current status
- Whether study treatment was discontinued
- The reason why the event is classified as serious
- Investigator assessment of the association between the event and study treatment

Within the following 7 days, the investigator will provide further information on the SAE or the unanticipated problem in the form of a written narrative. This should include a copy of the completed SAE form or Unanticipated Problem Form, and any other diagnostic information that will assist the understanding of the event. Significant new information on ongoing serious adverse events should be provided promptly to the DCC.

SAEs that are still ongoing at the end of the study period must be followed up to determine the final outcome. Any SAE that occurs after the study period and is considered to be possibly related to the study treatment or study participation should be recorded and reported immediately.

If a patient becomes pregnant while participating in the trial it will be reported as an adverse event and will trigger the collection of additional information about the pregnancy on the Pregnancy Report Form. Pregnancy outcomes will be collected, including the outcome of the infant and if the pregnancy was terminated. Study Staff should complete the Pregnancy Report form when they learn about a pregnancy, and follow-up with the participant and update the form when additional information is available about the baby. The Pregnancy Report form will be submitted to the University of Pennsylvania IRB, and to the local site IRB as required.

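### Section 8.2 ends mandatory adverse event reporting 4 weeks after the last dose, which conflicts with the sections that keep participants who stop drug in follow-up to Week 40

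*Combined protocol and SAP*

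**What the plan says.** Section 8.2 is the one place that states when adverse events have to be tracked and reported. The period opens with the first study procedures and closes with the end of treatment follow-up, which is set by the last dose: "For this study, the study treatment follow-up is 4 weeks following the last dose of study drug". Section 8.4 uses the same term, study period, for SAEs. It asks for prompt recording and reporting of "Any SAE that occurs after the study period and is considered to be possibly related to the study treatment" or to study participation. It states no duty for a later SAE judged unrelated.

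Two further passages are framed by being on drug. Section 8.3.1 says: "Participants will be contacted weekly during dose escalation and monthly while on treatment to assess for the occurrence of Adverse Events of Interest". Section 6.9 has serum potassium measured after initiation or a dose increase, "as well as monthly throughout the duration of treatment".

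Other sections keep people who have stopped drug under observation:

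- Section 4.4.2: "If study medication is discontinued study visits and procedures will continue unless the participant withdraws consent for follow-up".
- Section 6.6.1: "Patients who stop taking study medication are not considered early withdrawals and will be asked to continue to provide follow-up data on the study schedule".
- Section 7.3 asks that every participant, on or off treatment, have all scheduled outcome evaluations to the end of the study.
- Sections 6.5 to 6.7 place adverse event review at calendar weeks 8 to 40. None of these contacts depends on still taking drug.
- Section 8.3 has adverse events sought at each contact, and the table in Section 15.1 carries an adverse event review row across the study visits.

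**The concern.** The second group of passages governs attendance and procedures. Section 8 governs what has to be reported. A site could therefore hold every visit for a participant who stopped drug at week 6 and still regard an unrelated hospital admission at week 20 as outside the reporting period.

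That matters for two endpoints. Serious hypotension is a primary safety endpoint (Section 3.2.1) and requires hospital or emergency room care. The treatment-emergent composite (Sections 2.1 and 3.2.2) includes death, myocardial infarction, stroke and hospitalization. Such events happen largely outside the dialysis unit, so their capture is likely to depend on adverse event and SAE reports.

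Discontinuation is also linked to the outcomes. Sections 6.8 and 6.9 stop study drug at a third dose reduction for hypotension or hyperkalemia, and 6.9 also stops it at a stated potassium level. If the arms stop at different rates, any loss of reports after stopping would differ by arm. The primary analysis is intention to treat (Sections 7.3 and 7.4.1) and needs the same capture in all arms.

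**Working it through.** **Inputs.** Planned treatment is 36 weeks (Section 3.1: "such that the total duration of study medication is 36 weeks"). The 8.2 window runs to last dose + 4 weeks. The last scheduled contact is Week 40 (Section 6.7: "At the Week 40 visit (4 weeks after end of treatment), patients will be interviewed in person or by telephone").

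**Step 1: reproduce the plan's own figure.** For a participant who completes treatment, 36 + 4 = 40. The 8.2 window ends at Week 40, exactly where 6.7 puts the final contact. There is no conflict for completers.

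**Step 2: participants who stop early.** For a last dose at week s, the window closes at s + 4. The distance to Week 40 is 40 − (s + 4) = 36 − s weeks, or (36 − s)/40 of the 40-week schedule.

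| Last dose (week) | 8.2 window closes (week) | Weeks short of Week 40 | Share of 40 weeks |
|---|---|---|---|
| 2 | 6 | 34 | 85% |
| 6 | 10 | 30 | 75% |
| 12 | 16 | 24 | 60% |
| 24 | 28 | 12 | 30% |
| 30 | 34 | 6 | 15% |
| 36 | 40 | 0 | 0% |

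Under 4.4.2, 6.6.1 and 7.3 the distance is 0 in every row.

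**Step 3: what starts the clock.** Section 5.4 replaces active drug with masked placebo at some down-titration steps. That is still study drug, so it does not start the 4 weeks. Only true discontinuation does.

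**Step 4: which endpoints are exposed.** Potassium above 6.5 mEq/L is largely protected. Section 6.5 takes a monthly value from the dialysis unit record and draws blood if there is none, by calendar visit, although the wording of 6.9 points the other way. Serious hypotension and the hospital-based parts of the composite have no such scheduled measurement.

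**Step 5: an illustrative upper bound.** The documents give no rate of drug discontinuation. The 10% in Sections 7.1 and 7.3 is dropout or withdrawal from the study. Assume that stopping times are uniform over 36 weeks and that every site applies 8.2 literally. The mean stop is then week 18, the window closes on average at week 22, and (40 − 22)/40 = 45% of a stopper's schedule lies outside it. If 20% of spironolactone and 5% of placebo participants stop, the share outside is 0.20 × 0.45 = 9.0% against 0.05 × 0.45 = 2.25%. With 30% and 10% it is 13.5% against 4.5%. These are shares of follow-up time, not effects on event rates.

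**The case against.** The strongest reply is that the design plainly intends full follow-up, and says so repeatedly. Besides 4.4.2, 6.6.1 and 7.3, Section 5.6 keeps participants in follow-up when drug is withdrawn for a prohibited medication. Section 4.4.1 seeks consent to continue safety monitoring even after study consent is withdrawn. The contacts in 6.5 to 6.7 ask about the very events at issue, and 8.3, inside the safety section, has them sought every time. On this view 8.2 sets a minimum and tells nobody to stop.

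Much of this stands, and it rules out three stronger readings that a reader might infer:

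- **That participants who stop drug are followed for less time.** The documents do not say this. Visits, procedures and adverse event review continue by calendar. What is cut short on a literal reading is the stated reporting duty.
- **That hyperkalemia and hypotension are asked about only while on drug.** Section 8.3.1 gives a contact frequency and contains no such restriction. Week 40 is off treatment for everyone and still reviews adverse events.
- **That the resulting bias hides harm.** Neither size nor direction can be established. Lost reports would lower an incidence proportion, but Section 7.4.1 also plans incidence rates. If person-time were cut at the same point, those rates could move either way, since the lost time is more than 4 weeks off drug.

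The reply does not remove the conflict. Section 8.2 alone defines the mandatory period, 8.4 relies on that term to narrow what is reported afterwards, and no section gives precedence to 4.4.2, 6.6.1 or 7.3.

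**Conclusion.** The point holds as an internal contradiction over the reporting window for participants who discontinue study drug before week 36. Its size in time follows from the documents: 36 − s weeks for a stop at week s, and none for completers. Its effect on the safety results does not follow from them. That depends on how many participants stop, when, in which arm, and how many sites read 8.2 and 8.4 literally, and none of these is given. The time shares in Step 5 are an upper bound under assumed stopping rates.

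The exposure falls on serious hypotension and the treatment-emergent composite rather than on potassium above 6.5 mEq/L. It should be corrected because safety is the main purpose of this pilot, discontinuation is partly driven by the safety outcomes, and the correction is small.

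**What to change.** State one adverse event and SAE collection window in Section 8.2 for every randomized participant who has not withdrawn consent, whether or not still on drug: through the Week 40 contact or 4 weeks after the last dose, whichever is later. The second limb is useful because the Week 36 and Week 40 visits each have a window of 7 days either side. A last dose at week 37 and a final contact at week 39 would be only 2 weeks apart.

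Then align the rest:

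- In 8.3.1, tie the contacts to the study schedule rather than to treatment status.
- In 8.4, make the study period the window defined in 8.2, so that the relatedness condition applies only after it closes.
- Reconcile the potassium wording in 6.9 with the calendar-based collection in 6.5. This concerns outcome collection only; clinical monitoring remains for the sponsor to settle.
- Keep last dose plus 4 weeks as a separately named on-treatment period for analysis, so that the intention-to-treat and on-treatment summaries use the same collected data.

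The cost is a wording amendment and a note to sites. The contacts are already scheduled.

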8.2.1. Post-study Adverse Event

All unresolved adverse events will be followed by the investigator until the events are resolved, the participant is lost to follow-up, or the adverse event is otherwise explained. At the last scheduled visit, the investigator will instruct each participant to report any subsequent event(s) that the participant, or the participant's personal physician, believes might reasonably be related to participation in this study. The investigator will notify the DCC of any death or adverse event occurring at any time after a participant has discontinued or terminated study participation that may reasonably be related to the study. The sponsor (NIDDK) will also be notified if the investigator should become aware of the development of cancer or of a congenital anomaly in a subsequently conceived offspring of a participant that has participated in this study.

8.3. Recording of Adverse Events

At each contact with the participant, the investigator or site designee will seek information on adverse events by specific questioning and, as appropriate, by examination. Information on adverse events will be recorded in the source document, and also on the adverse event log

case report form (CRF). All signs, symptoms, and abnormal diagnostic procedure results relating to the same event will be recorded under one diagnosis name.

